### Protocol Change Status

Protocol Revision #	Revision Date
Revision A	December 21, 2009
Revision B	February 25, 2010
Revision C	May 13, 2010
Revision D	March 14, 2011
Revision E	July 8, 2011
Revision F	November 11, 2011

## 1 SYNOPSIS

Study Number:	2008-07									
Title:	Magna Mitral 23 Clinical Evaluation of the size 23 mm Carpentier–Edwards PERIMOUNT Magna Mitral Bioprosthesis, Model 7000TFX									
Purpose:	The purpose of this clinical study is to obtain human clinical data that demonstrates that the size 23 mm Carpentier–Edwards PERIMOUNT Magna mitral pericardial valve, model 7000TFX, is a safe and effective replacement heart valve.									
Study Device:	
Carpentier–Edwards PERIMOUNT Magna mitral pericardial valve, model 7000TFX, size 23 mm (Magna mitral valve, size 23 mm)
 
The size 23 mm Magna mitral valve is one size smaller than the Magna mitral valve, size 25 mm approved by FDA in August 2008. The Magna mitral valve, size 23 mm would be implanted in same size mitral annulus as the size 27 mm porcine Carpentier–Edwards Duraflex mitral low pressure valve, model 6625LP, as shown below in Table A. The Duraflex valve was approved by FDA in September 1991.
 
Table A: Valve dimension comparison
 
  
 Dimension	Model 7000TFX, 23 mm	Model 6625LP, 27 mm	
   
 Tissue Annulus diameter (TAD)*	27 mm	27 mm	
 
 External Sewing Ring Diameter	34 mm	36 mm	
  
 
* Note TAD corresponds to the “External Stent Post Diameter (Base)” in the Model 7000TFX, size 23 mm IFU and the “Mounting Diameter (Annulus)” in the Model 6625LP IFU.
	Dimension	Model 7000TFX, 23 mm	Model 6625LP, 27 mm	Tissue Annulus diameter (TAD)*	27 mm	27 mm	External Sewing Ring Diameter	34 mm	36 mm
Dimension	Model 7000TFX, 23 mm	Model 6625LP, 27 mm								
Tissue Annulus diameter (TAD)*	27 mm	27 mm								
External Sewing Ring Diameter	34 mm	36 mm								
Intended Use:	The Carpentier–Edwards PERIMOUNT Magna mitral pericardial valve, model 7000TFX, is indicated for patients who require replacement of their native or prosthetic mitral valve.									


Study Objective:
	
The objective of this study is to evaluate the safety and effectiveness of the size 23 mm Magna mitral valve in subjects with mitral heart valve disease requiring replacement with a valve. Data collected in this study will be used to support the premarket application for approval in the United States. This study may also be used to support device approval in other countries as applicable.

Overall Design and Duration:
	
This is a prospective, non-randomized, multi-site, descriptive study. A minimum of 15 and up to 20 subjects will be implanted at a minimum of 2 and up to 8 participating investigational sites, within the US and internationally. Subject participation will last for 5 years. Subjects will be assessed for clinical follow-up at the following intervals: pre-study procedure, at implant, index hospitalization discharge, 6 months post procedure, 1 year post procedure and annually thereafter until 5 years post procedure or death, whichever occurs first. Safety and effectiveness data for Edwards Lifesciences Carpentier-Edwards PERIMOUNT Plus Pericardial Bioprosthesis, Mitral Model 6900P from Protocol 98-1 will be used to generate a general comparison with the size 23mm Magna mitral valve data from this IDE protocol.

Study Population:
	
Male and female diagnosed with mitral heart valve disease and scheduled to undergo elective mitral valve replacement with a smaller bioprosthetic are eligible for participation in the study.
 
Key Inclusion Criteria
 
 
- Patient is 13 years of age or older;
 
- Patient has mitral valve disease requiring planned surgical replacement;
 
- Patient has provided written informed consent prior to mitral valve surgery;
 
- Patient is willing to comply with specified follow-up evaluations.
 
 
Key Exclusion Criteria
 
 
- Patient has life expectancy < 12 months due to non-cardiac co-morbid conditions;
 
- Patient has/had active endocarditis within the last 3 months;
 
- Patient has a body surface area (BSA) >1.9 m^2;
 
- Patient requires replacement of a native or previously
 

	
implanted prosthetic tricuspid, pulmonic, or aortic valve;
 
 
- Patient has/had prior aortic, tricuspid and/or pulmonary valve surgery, which included implant of a bioprosthetic valve or mechanical valve that will remain in situ.
 

Safety Endpoints:
	
The following adverse events will be reported for the safety analysis:
 
 
- Thromboembolism
 
- Valve thrombosis
 
- All hemorrhage
 
- Major hemorrhage
 
- All perivalvular leak
 
- Major perivalvular leak
 
- Endocarditis
 
- Hemolysis
 
- Structural valve deterioration
 
- Non-structural valve dysfunction
 
- Reoperation
 
- Explant
 
- Death
 
- Valve-related death
 
 
Blood Data to evaluate valve-related hemolysis collected preoperatively, at 6-month, 1-year, and every yearly follow-up visit will be analyzed and presented by time period.

Effectiveness Endpoints:
	
The following are the effectiveness endpoints:
 
 
- Mean effective orifice area (EOA) at 1 year post-implant
 
- Number and percentages of subjects in NYHA functional class I or II at 1 year post-implant
 
 
Hemodynamic Performance
 
The pre-procedure and 1-year post-procedure NYHA distribution (numbers and percentages of subjects) will be tabulated. Number and percentage of subjects in NYHA functional class I or II at 1 year post-implant will be reported. NYHA functional class will be obtained at each follow-up time-point, and the numbers and percentages of subjects who have improved in class, not changed in class, and worsened in class will be reported.
 
Hemodynamic Performance at 1 year post implant:

	
 
- Peak gradient
 
- Mean gradient
 
- Effective orifice area (EOA) index
 
- Performance index
 
- Cardiac output
 
- Cardiac index
 
- Severity of mitral regurgitation
 
- Left ventricular mass regression(data collected for research; not required for endpoint evaluation)
 
 
Quality of Life Survey (EQ-5D) at 6 and 12 months post-implant as compared to baseline measurements prior to implant.

General Statistical Methods	The format used to support the 3/26/02 approval of the size 29mm Edwards Lifesciences Prima Plus aortic valve, via P00007/S002 will serve as a guide for data presentation.
Principal Investigator:	[REDACTED]
Study Sponsor	[REDACTED]
Study Monitor	Edwards Lifesciences, LLC [name]
DMC Chair:	[REDACTED]
Core Lab:	[REDACTED]

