## 2 INTRODUCTION

### 2.1 CLINICAL BACKGROUND

#### 2.1.1 DISEASE PROCESS

Valvular heart disease is a life-threatening disease that afflicts millions of people worldwide and leads to approximately 250,000 valve repairs and/or replacements each year. Mitral valvular heart disease is a condition that may include stenosis, regurgitation, or combination of the two, sometimes referred to as mixed disease.

Stenosis of the mitral valve is the narrowing of the valve opening that causes lower blood flow through the valve. In over 99% of stenotic mitral valves, the etiology is rheumatic disease. Other rare causes of mitral stenosis include congenital malformed valves, active infective endocarditis, massive annular calcium, and metabolic or enzymatic abnormalities. Regurgitation of the mitral valve occurs when blood flows back into the valve as the leaflets close or leaks through the leaflets after they are closed. Mitral regurgitation has multiple etiologies including: floppy mitral valves, active or healed infective endocarditis, papillary muscle dysfunction, annular calcium, idiopathic chordae tendineae rupture, rheumatic disease, dilated and hypertrophic cardiomyopathies, endocardial fibrosis, collagen-vascular disorders (lupus, scleroderma), or Marfan's or Marfan-like disorders. As the incidence of rheumatic mitral stenosis and regurgitation has decreased, mitral regurgitation caused by degenerative disease of the mitral apparatus and caused by the left ventricular dysfunction associated with coronary artery disease has become the predominant hemodynamic lesion of the mitral valve. Edward et. al. reviewed data collected from 1648 patients between January 1990 and December 1999 in northern New England, and noted that mitral valve replacements and repair procedures have substantially increased and indications for these procedures have expanded to also include older and sicker patients with less rheumatic and more degenerative and coronary artery-related mitral valve problems.

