**Table 7: Follow-up Evaluation**

General Information	Clinical Information	Blood Studies	Echocardiography
Subject ID Number Subject Initials Date of Evaluation Visit Status	Patient Status Physical Assessment Cardiac Rhythm NYHA Functional Class Antithromboembolic therapy Adverse Events	Blood Draw Date White Blood Cell Count Red Blood Cell Count Hemoglobin Hematocrit Platelet Count Plasma Free Hemoglobin	Date of exam 2D measurements  Ejection fraction Mitral valve assessment  LVOT assessment Aortic Valve assessment  Other Variables  Left Ventricular Assessment 

At each postoperative assessment, the Investigator(s) will need to determine the subject's availability for future follow-up. If any subject needs to be seen at a time other than a regularly scheduled follow-up visit, the same information as described above will be documented by the Investigator and indicated as an interim visit. Follow-up information obtained by physicians outside of the investigational site should be obtained by the Investigator.

 2-Dimensional measurements are Interventricular Septal thickness (IVS), Left Ventricular Internal Diameter in diastole (LVEDD), end diastolic Posterior Wall thickness (PW), Left Ventricular Internal Diameter in systole (LVESD), Left Atrium (LA), Left Ventricular Outflow Tract (LVOT)

 Mitral valve assessment includes the following parameters Mitral Valve Peak Flow Velocity (VmaxMV), Mean Pressure Gradient: Mitral Valve (MPG MV), Peak Pressure Gradient: Mitral Valve (PPG MV), Mitral Valve Time Velocity Integral (TVI MV), presence of Stenosis, presence and degree of Regurgitation

 Aortic valve assessment includes the following parameters Aortic Valve Peak Flow Velocity (VmaxAV), Mean Pressure Gradient: Aortic Valve (MPG AV), Aortic Valve Time Velocity Integral (TVI AV)

 Other variables includes the following parameters which are calculated by the echo machine Stroke Volume (SV), Cardiac Output (CO), Cardiac Index (CI), Effective Orifice Area: Mitral Valve (EOA MV)

 Left ventricular Assessment includes presence of wall motion abnormality, thrombi, pericardial effusion and other relevant clinical findings

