### **ANALYSIS POPULATION**

The primary safety and effectiveness analyses will include all the implanted subjects. All the data collected up to the point of the explant or expirations will be included in the safety and effectiveness analyses.

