## 11.2 EFFECTIVENESS ANALYSIS

### 11.2.1 EFFECTIVENESS ENDPOINTS

Mean effective orifice area (EOA) at 1 year post-implant will be reported. The pre-procedure and 1 year post-procedure NYHA distribution (numbers and percentages of subjects) will be tabulated. Number and percentage of subjects in NYHA functional class I or II at 1 year post-implant will be reported. NYHA functional class will be obtained at each follow-up time-point, and the numbers and percentages of subjects who have improved in class, not changed in class, and worsened in class will be reported.

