#### 11.2.1.1 Hemodynamic Performance

Echocardiography data will be obtained preoperatively, at discharge, 6-months and 1 year, 2 year, 4 year, and 5 year follow-up visits. The echocardiographic hemodynamic parameters to be evaluated are peak gradient, mean gradient, effective orifice area (EOA), EOA index, performance index, cardiac output, cardiac index, left ventricular mass regression (data collected for research; not required for endpoint evaluation), and valvular regurgitation. Descriptive statistics for the continuous echo variables and change from baseline (e.g. mean, standard deviation, and range) categorized by follow up time intervals will be reported. Regurgitation data will be summarized by frequencies at each pre-procedure severity level.

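### Change from baseline in effective orifice area (EOA) is pooled across regurgitant and stenotic subjects; if EOA is flow-based, a removed leak counts as orifice gain and the pooled mean can have the wrong sign

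*Combined protocol and SAP*

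**What the plan says.** Section 11.2.1.1 (Hemodynamic Performance) lists EOA and EOA index among the echo parameters and plans "Descriptive statistics for the continuous echo variables and change from baseline (e.g. mean, standard deviation, and range) categorized by follow up time intervals". Follow-up interval is the only grouping. On leaks, the same section says "Regurgitation data will be summarized by frequencies at each pre-procedure severity level"; nothing links that table to EOA.

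The Analysis Population paragraph of Section 11 states "The primary safety and effectiveness analyses will include all the implanted subjects". The Synopsis lists "Mean effective orifice area (EOA) at 1 year post-implant" first among the effectiveness endpoints, and Section 11.2.1 names the same endpoint: "Mean effective orifice area (EOA) at 1 year post-implant will be reported". Change in EOA is not itself an endpoint.

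The footnotes to Tables 3, 5 and 7 list an LVOT dimension, the mitral time-velocity integral (TVI), and the presence and degree of mitral regurgitation. Stroke volume and mitral EOA are listed as values computed by the ultrasound system. No pressure half-time or planimetered area is listed. Section 8.8 leaves echo evaluation to an Echo Protocol (Section 17.8), which is not in the text available for review.

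On the disease, Section 2.1.1 allows stenosis, regurgitation or both, and says that mitral regurgitation of degenerative or ischemic origin "has become the predominant hemodynamic lesion of the mitral valve".

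**The concern.** A flow-based EOA equals the orifice area only if the volume measured in the outflow tract is the volume that crossed the mitral valve. When the native valve leaks, part of the mitral inflow returns to the atrium and never reaches the outflow tract, so the ratio is too small. After replacement the leak is normally gone and the ratio is about right. The difference between the two visits then mixes the change in orifice with the disappearance of the leak.

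This study concerns a valve one size below the smallest approved size in its line, so a reader will look for evidence that the opening is too small. A pooled table that shows a gain in EOA, when the prosthesis is in truth smaller than the average native opening, would point that reader the wrong way.

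**Working it through.** The plan gives no EOA value, standard deviation, lesion mix or formula, so there is no figure of its own to reproduce. All areas, fractions and shares below are assumptions. The check takes the recorded variables at face value and uses conservation of flow.

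**Formula.** Let A be the true mitral area, RV the mitral regurgitant volume and RF = RV / (A x TVI).
- Reported EOA = LVOT stroke volume / mitral TVI.
- Mitral inflow per beat = A x TVI = LVOT stroke volume + RV, with no aortic leak.
- Hence reported EOA = A x (1 - RF). EOA index, taken as EOA over body surface area, carries the same factor.

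**One regurgitant subject.** With native area A0 and a non-leaking prosthesis of area A1, the change has the wrong sign when A0 x (1 - RF) < A1 < A0, that is, when RF > 1 - A1/A0. For A1 = 1.6 cm2:
- A0 = 2.0: 1 - 1.6/2.0 = 20%
- A0 = 3.0: 1 - 1.6/3.0 = 47%
- A0 = 4.0: 1 - 1.6/4.0 = 60%
- A0 = 5.0: 1 - 1.6/5.0 = 68%

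Below the threshold the sign is right but the size can be far off. With A0 = 4.0 and RF = 50%, the reported change is 1.6 - 2.0 = -0.4 cm2 and the true change is 1.6 - 4.0 = -2.4 cm2.

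**Pooled mean.** Let a share p be regurgitant (A0 = 4.0, RF = 50%) and the rest purely stenotic (native area 1.0), with A1 = 1.6. The upward bias is p x A0 x RF.

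| p | True change | Reported change |
|---|---|---|
| 30% | 1.6 - (0.3 x 4.0 + 0.7 x 1.0) = -0.30 | 1.6 - (0.3 x 2.0 + 0.7 x 1.0) = +0.30 |
| 50% | 1.6 - 2.5 = -0.90 | 1.6 - 1.5 = +0.10 |
| 70% | 1.6 - 3.1 = -1.50 | 1.6 - 1.7 = -0.10 |

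The true change is zero at p = 0.6/3.0 = 20% and the reported change is zero at p = 0.6/1.0 = 60%. Between those shares the pooled sign is wrong.

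**Range.**
- With the same areas, the wrong-sign interval is 20-33% at RF 30%, 20-43% at RF 40% and 20-100% at RF 60%.
- With RF 50% and A0 = 4.0, it is 7-20% for a 1.2 cm2 prosthesis and 33-100% for a 2.0 cm2 prosthesis.

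**With between-subject spread.** A simulation at n = 15 and n = 20 used regurgitant A0 4.0 (SD 0.6), RF 50% (SD 10%), stenotic A0 1.0 (SD 0.2) and A1 1.6 (SD 0.3). The pooled change was positive when the true change was negative in 74-80% of trials at a 30% regurgitant share, 71-74% at 50% and 27-29% at 70%.

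**The case against.** The strongest objection is that the method is unseen. The Echo Protocol may specify another way to obtain EOA, or may make EOA unreportable when the valve leaks, and then there would be no biased value to pool. The recorded lists do not settle this. They omit pressure half-time, but they also omit the LVOT time-velocity integral that the assumed ratio needs, which has to be read into an undefined LVOT assessment. The source of stroke volume is not given either. If it came from left ventricular dimensions it would include the regurgitant volume, and the bias would vanish. All of this stands, so the conclusion is conditional.

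The lesion mix is also unknown. Section 2.1.1 speaks of mitral disease in general, and Section 2.1.2 says that repair is usually preferred, so the share of regurgitation among patients who receive a replacement valve could differ.

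A reader might infer three stronger things that the documents do not support:
- **That the 1-year mean EOA has the wrong sign or is badly biased.** A mean has no sign, and only a leak present at 1 year affects it: mitral or perivalvular leak lowers it, aortic leak raises it. If 3 of 15 subjects had a 20% aortic regurgitant fraction, each would read 1/(1 - 0.2) = 1.25 times too high, and the mean would shift by 3/15 x 25% = 5%, or 0.08 cm2 at 1.6. Its standard error is 0.08 to 0.13 cm2 for an assumed SD of 0.3 to 0.5.
- **That aortic regurgitation goes unrecorded.** It is not in the aortic footnotes, but Section 11.2.1.1 covers valvular regurgitation without naming a valve, and the case report forms are not visible.
- **That subjects with a mitral leak at 1 year should be excluded from the EOA mean.** That leak can be an outcome of the device, so excluding on it would select favorable subjects.

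The study is descriptive and tests no hypothesis, so no error rate is at risk. But its descriptive tables are its whole output, and Section 11 sets them beside data from Protocol 98-1. Prosthesis performance can still be judged from 1-year EOA, gradients and regurgitation grade, which limits the harm to the change-from-baseline rows.

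**Conclusion.** The concern holds for change from baseline in EOA and EOA index, on condition that EOA is LVOT stroke volume over mitral TVI. That is the natural reading of the recorded variables but is not stated. Under it, pre-procedure EOA is understated by the mitral regurgitant fraction, and change from baseline is biased upward in regurgitant subjects. The pooled mean can show a gain where there was a loss: +0.30 against -0.30 cm2 in the example with a 30% regurgitant share. A wrong sign is possible, not certain; it depends on a lesion mix and on areas that the documents do not give. The 1-year mean EOA, which is the endpoint, is a separate and smaller matter and needs no change.

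**What to change.** In Section 11.2.1.1, add that change from baseline in EOA and EOA index will be reported separately by pre-procedure mitral regurgitation severity. That grade is already collected and is already used for the regurgitation table. State that neither the pooled change nor the change in subjects with more than mild pre-procedure regurgitation will be interpreted as a change in orifice size, and that observed follow-up values will be used for those subjects.

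Keep the all-subject 1-year mean EOA as the endpoint. Optionally, list each subject's 1-year EOA beside the regurgitation grade at that visit, with no exclusions. If the Echo Protocol uses a method that a mitral leak does not affect, a sentence saying so in Section 11.2.1.1 would settle the point without the split.

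The cost is a few table rows and no new visits, measurements or subjects. The downside is small strata: a 30% share of 15 to 20 subjects is only about 5 or 6 people (0.3 x 15 = 4.5; 0.3 x 20 = 6), so individual values may say more than stratum means.

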## 2 INTRODUCTION

### 2.1 CLINICAL BACKGROUND

#### 2.1.1 DISEASE PROCESS

Valvular heart disease is a life-threatening disease that afflicts millions of people worldwide and leads to approximately 250,000 valve repairs and/or replacements each year. Mitral valvular heart disease is a condition that may include stenosis, regurgitation, or combination of the two, sometimes referred to as mixed disease.

Stenosis of the mitral valve is the narrowing of the valve opening that causes lower blood flow through the valve. In over 99% of stenotic mitral valves, the etiology is rheumatic disease. Other rare causes of mitral stenosis include congenital malformed valves, active infective endocarditis, massive annular calcium, and metabolic or enzymatic abnormalities. Regurgitation of the mitral valve occurs when blood flows back into the valve as the leaflets close or leaks through the leaflets after they are closed. Mitral regurgitation has multiple etiologies including: floppy mitral valves, active or healed infective endocarditis, papillary muscle dysfunction, annular calcium, idiopathic chordae tendineae rupture, rheumatic disease, dilated and hypertrophic cardiomyopathies, endocardial fibrosis, collagen-vascular disorders (lupus, scleroderma), or Marfan's or Marfan-like disorders. As the incidence of rheumatic mitral stenosis and regurgitation has decreased, mitral regurgitation caused by degenerative disease of the mitral apparatus and caused by the left ventricular dysfunction associated with coronary artery disease has become the predominant hemodynamic lesion of the mitral valve. Edward et. al. reviewed data collected from 1648 patients between January 1990 and December 1999 in northern New England, and noted that mitral valve replacements and repair procedures have substantially increased and indications for these procedures have expanded to also include older and sicker patients with less rheumatic and more degenerative and coronary artery-related mitral valve problems.

### 2.1.2 ALTERNATIVE THERAPIES/TECHNIQUES

Diseased heart valves can be treated by medication, surgical repair and surgical replacement. Repairing the native valve is generally preferred over replacing it. Surgical repair can involve modifying the valve tissue or underlying structures. This procedure can be performed with or without implant of an annuloplasty ring that provides support to the native valve so that it closes completely and functions normally. If the native valve cannot be repaired, it is replaced by either a mechanical (constructed from synthetic material) or a tissue bioprosthetic valve (made primarily from animal tissue including bovine pericardium, or human valves from cadavers).

The Society of Thoracic Surgeons (STS) published an Executive Summary quantifying major cardiac surgical procedures performed in the United States throughout a 10 year period from 1998 to 2007. The data showed an average of 4,339 isolated mitral valve replacements are performed per year. The Starr-Edwards ball-and-cage mitral valve was the first commercially available reliable device for mitral valve replacement. This device was first implanted in a 52 year old patient in 1960. Since then, many generations of both mechanical and bioprosthetic valves have emerged. As the first, second and third generations of mechanical prosthetic valves were being developed; bioprosthetic replacement valves were simultaneously being developed. The advantages of bioprosthetic valves include a much lower frequency of thromboembolism; subsequently, long-term anticoagulation therapy can be avoided. The third generation of these valves included pericardial valves which incorporated new technology aimed at improving valve longevity and hemodynamic function.

Currently, there are no commercially approved bovine pericardial tissue mitral valves with the same or similar dimensions as the size 23 mm Magna mitral valve.

